## 4.2 CONCOMITANT THERAPY, RESTRICTIONS, AND RESCUE TREATMENT

## 4.2.1 Rescue medication, emergency procedures, and additional treatments

Rescue medication to reverse the action of BI 836826 is not available. Potential side effects of BI 836826 have to be treated symptomatically. Patients should receive supportive care according to local guidelines regarding treatment of infusion-related reactions, blood product support, antibiotics, antivirals, analgesics, skin and mouth care, etc. In the case of a tumour lysis syndrome, supportive therapy including rasburicase may be used as clinically indicated at the investigator's discretion. The use of growth factors such as granulocyte colony stimulating factor (G-CSF) will be allowed, but growth factors should be avoided in the first treatment course for better assessment of safety and response parameters.

CMV reactivation during treatment should be treated according to local standards or available guidelines (R10-4431).

All concomitant non-antileukaemia therapies to provide adequate care may be given as clinically necessary. All concomitant treatments should be recorded in the eCRF except for vitamins or nutrient supplements. Trade name, indication and dates of administration of concomitant therapies will be documented. For parenteral nutrition during the trial, the components need not to be specified in detail. It should just be indicated as 'parenteral nutrition'. If a patient needs anaesthesia, it will be sufficient to indicate 'anaesthesia' without specifying the details.

Concomitant therapy should be recorded in the eCRF during the screening and treatment period, starting at the date of signature of informed consent, and ending at the EOT-visit. After the EOT-visit, only concomitant therapy indicated for treatment of an adverse event has to be reported.

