**Trial Protocol** 

5.1.2.3 Blood counts (red blood cells, haemoglobin, platelets, neutrophils)

• Blood counts including a differential will be done at all visits. In patients with blood counts below the limits of normal pre-treatment, improvement in blood counts during therapy may indicate a benefit for the patient.

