5.1.2.4.1 Complete remission (CR)

CR requires all of the following criteria for a period of at least 2 months:

- A1 Peripheral blood lymphocytes (evaluated by WBC and differential count) below  $4 \times 10^9$ /L.
- A2 Absence of significant lymphadenopathy, i.e. no lymph nodes > 1.5 cm.
- A3 No hepatomegaly.
- A4 No splenomegaly.
- A5 Bone marrow aspirate and biopsy demonstrate absence of residual disease.
- B1 Platelets more than  $100 \times 10^9$ /L (without exogenous growth factors or transfusion).
- B2 Hemoglobin more than 110 g/L (without exogenous growth factors or transfusions)
- B3 Neutrophils more than  $1.5 \times 10^9$ /L (without exogenous growth factors).
- C Absence of disease-related constitutional symptoms.
- 4.

Group A criteria define the tumor load, group B criteria define the function of the hematopoietic system. In case all criteria A and C are met, but a patient has a persistent anemia or thrombocytopenia or neutropenia apparently unrelated to CLL, but related to drug toxicity, the patient should be categorized as CR with incomplete marrow recovery (CRi).

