#### 5.1.2.4.3 Partial remission (PR)

To define a PR, at least 2 criteria of category A and 1 criterion of category B have to be met for a period of at least 2 months.

- A1 Decrease in the number of blood lymphocytes by 50% or more compared to the pretreatment value.
- A2 Reduction in lymphadenopathy by 50% or more, defined as a decrease in lymph node size by 50% or more, either in the sum products of up to 6 lymph nodes or in the largest diameter of the enlarged lymph nodes detected prior to therapy, AND no increase in any lymph node, and no new enlarged lymph node. In small lymph nodes

(<2cm) an increase of less than 25% is not considered to be significant.

- A3 Decrease in hepatomegaly by 50% or more
- A4 Decrease in splenomegaly by 50% or more.
- A5 Reduction by 50% or more in bone marrow infiltration, or B-lymphoid nodules.
- B1 Platelets more than  $100 \ge 10^9$ /L or 50% improvement over baseline (without exogenous growth factors or transfusion).
- B2 Hemoglobin more than 110 g/L or 50% improvement over baseline (without exogenous growth factors or transfusions).
- B3 Neutrophils more than  $1.5 \ge 10^9$ /L or 50% improvement over baseline (without exogenous growth factors).
- 5.1.2.4.4 Progressive disease (PD)

At least one of the following criteria is required:

- A1 An increase in the number of blood lymphocytes by 50% or more over baseline with an absolute number of B-lymphocytes of at least  $5 \times 10^9$ /L.
- A2 Progression of lymphadenopathy, defined as appearance of any new lymph node > 1.5 cm or an increase by 50% or more in the greatest determined diameter of any previous site, or appearance of a new organ infiltrate other then hepatomegaly or splenomegaly.
- A3 An increase in the previously noted enlargement of the liver by 50% or more or new appearance of hepatomegaly.
- A4 An increase in the previously noted enlargement of the spleen by 50% or more or new appearance of splenomegaly.
- B1 Decrease of platelet counts by more than 50% or to less than  $100 \times 10^9$ /L secondary to CLL and unrelated to autoimmune cytopenia
- B2 Decrease of hemoglobin levels by more than 20 g/L or to less than 100 g/L secondary to CLL and unrelated to autoimmune cytopenia
- T Transformation to a more aggressive histology, e.g. Richter syndrome.

During therapy, cytopenia cannot be used to define disease progression. The progression of any cytopenia unrelated to autoimmune cytopenia as defined by criteria B1 and B2 which

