5.2.2 Other Secondary endpoints

Note: For the response/efficacy analyses with respect to overall response assessment by investigator used: If patients would have their examinations contributing to the disease assessment over a number of days, the earliest date of the multiple examinations should be considered.

For the response/efficacy analyses with respect to lymphocytes and blood counts only laboratory data assessed >= 8 days after the last infusion and with reported laboratory response assessment on-treatment and before start of new Chronic Lymphocytic Leukaemia (CLL) therapy is used. The reason for this approach is that otherwise the respective values of lymphocytes and blood counts would be biased due to the infusion after which an immediate change in values of the respective blood parameters is observed. This change though does not reflect an efficacy effect.

Number of lymphocytes in the peripheral blood

The secondary endpoint with respect to number of lymphocytes in the peripheral blood is defined as "Best % change from baseline in number of lymphocytes in the peripheral blood".

Blood counts (haemoglobin, platelets, neutrophils)

The secondary endpoints with respect to blood counts are defined as

- "Number of patients with improved haemoglobin count for at least two subsequent response assessments"
- "Number of patients with improved platelet count for at least two subsequent response assessments"
- "Number of patients with improved neutrophil count for at least two subsequent response assessments"

An improvement is indicated by the fulfilment of the criteria for "Complete Remission" or "Partial Remission", i.e.

- Haemoglobin count: Greater than 11g/dL or increase of 50% or more compared to baseline if haemoglobin is less than or equal to 11g/dL
- Platelet count: Greater than 100 000/ μ L or increase of 50% or more compared to baseline if platelets are less than or equal to 100 000/ μ L
- Neutrophil count: Greater than 1500/ μL or increase of more than 50% compared to baseline if neutrophil count is less than or equal to $1500/\mu L$

Best overall response:

Response will be assessed according to the NCIWG guidelines (R10-4429) based on laboratory data from the peripheral blood and clinical examination by the investigator. Each patient will be assigned to one of the following categories:

- complete remission (CR)
- complete remission with incomplete marrow recovery (CRi)
- partial remission (PR)
- stable disease (SD)

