7.5.2 Secondary endpoints

Number of lymphocytes in the peripheral blood

The number of lymphocytes in the peripheral blood will be analyzed in terms of the best percentage change from baseline until start of subsequent CLL therapy or PD. Best percent change is thereby derived by taking the difference between the baseline value and the minimum of all observed values over time. For the primary analysis of this endpoint, summary statistics will be presented for all patients of the TS by dose cohort and in total. In addition, summary statistics will be presented separately for patients of the TS with an abnormal and normal lymphocyte count at baseline. An abnormal baseline count is defined as a lymphocyte count $> 4*10^9$ /L. In addition, the following will be analysed:

Summary statistics will additionally be presented for minimum values of certain lymphocyte types (CD19+ B-cells, CD3+ T-cells, CD4+ T-cells, CD8+ T-cells and CD56+ NK-cells).

For CD4+ T-cells and CD19+ B-cells, the lowest count since start of treatment (nadir) and the time point of occurrence of (nadir) will be derived and described by summary statistics for all dose cohort together and separated by dose cohort. The association of values at baseline and values at nadir will be displayed graphically.

A waterfall plot will also be generated to summarise reduction of lymphocytes graphically and lymphocyte values will be graphically displayed over time for patients of the Treated Set. Furthermore, the number of lymphocytes and the change in lymphocyte count from baseline will be listed by time point.

Blood counts (haemoglobin, platelets, neutrophils)

[figure not shown]
A frequency table will be given for the endpoints "Number of patients with improved haemoglobin / platelet / neutrophil count for at least 2 subsequent response assessments" for all patients of the Treated Set. Additionally, graphical presentations of mean values of haemoglobin, platelet and neutrophil counts over time will be provided by dose cohorts. For neutrophils, the nadir and the time point of occurrence of nadir will be derived and described by summary statistics for all dose groups together and separated by dose group. The association of values at baseline and at time to nadir will be displayed graphically.

[figure not shown]
Best overall response

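### The three 'improved blood count' endpoints set no baseline condition on the absolute threshold, so patients who start above it are counted as improved even when their counts fall

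*SAP*

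**What the plan says.** SAP 4.1 replaces the protocol's secondary endpoint of blood counts with three counts of patients improved at two or more later response assessments. SAP 5.2.2 introduces the rule with "An improvement is indicated by the fulfilment of the criteria for" complete or partial remission, and then spells it out. For haemoglobin it reads "Haemoglobin count: Greater than 11g/dL or increase of 50% or more compared to baseline if haemoglobin is less than or equal to 11g/dL". Platelets and neutrophils follow the same two-limb form at 100 000/µL and 1500/µL. SAP 7.5.2 gives a frequency table for improved "haemoglobin / platelet / neutrophil count for at least 2 subsequent response assessments", for all patients of the Treated Set.

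Three other places bear on this:

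- Protocol 5.1.2.3 gives the reason for looking at these counts: "In patients with blood counts below the limits of normal pre-treatment, improvement in blood counts during therapy may indicate a benefit for the patient".
- For lymphocytes, SAP 7.5.2 does separate patients by baseline status: "summary statistics will be presented separately for patients of the TS with an abnormal and normal lymphocyte count at baseline". It has no such split for haemoglobin, platelets or neutrophils.
- The protocol's remission criteria qualify the haemoglobin limb: "Hemoglobin more than 110 g/L (without exogenous growth factors or transfusions") for CR, and "Hemoglobin more than 110 g/L or 50% improvement over baseline (without exogenous growth factors or transfusions") for PR. The SAP list drops the qualifier on growth factors and transfusions.

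**The concern.** The remission thresholds describe a state: the count is adequate. The SAP uses them to label a change. A patient who enters above the threshold and stays above it meets the rule at every assessment, whether the count rises, holds or drops.

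Such patients can enrol. Protocol 3.3.3 sets only lower entry limits for neutrophils (1.0 x 10^9/L) and platelets (25 x 10^9/L), and no haemoglobin limit is listed. Progressive marrow failure is only one of five alternative ways to show active disease under inclusion criterion 3.

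The table therefore cannot show whether any low count recovered. Differences between small dose cohorts would follow their baseline mix. Falling counts are also a realistic direction here, since the protocol's DLT definition includes prolonged grade 4 neutropenia and thrombocytopenia. A patient with a marked fall in neutrophils could appear in an efficacy table as improved.

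**Working it through.** **1. How the rule reads.** The documents state no expected figure for these endpoints, so there is none to reproduce. The trailing 'if' clause can be read in three ways:

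- (A) it refers to the current value and belongs to the second limb only;
- (B) it refers to the baseline value and belongs to the second limb only;
- (C) it refers to the baseline value and governs both limbs.

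Over a grid of baseline and on-treatment values, A and B classified every pair identically for all three parameters. Only C gives a different answer.

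| Baseline to on-treatment | Change | A and B | C |
|---|---|---|---|
| Hb 14 to 11.5 g/dL | -18% | improved | not |
| Hb 13 to 13 g/dL | 0% | improved | not |
| Hb 9 to 10.5 g/dL | +17% | not | not |
| Hb 10.8 to 11.1 g/dL | +3% | improved | improved |
| Platelets 250 to 110 x10^9/L | -56% | improved | not |
| Platelets 60 to 80 x10^9/L | +33% | not | not |
| Neutrophils 5.0 to 1.6 x10^9/L | -68% | improved | not |

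**2. What the 50% limb adds.** It matters only when 1.5 x baseline does not exceed the threshold. That means baseline haemoglobin at or below 11/1.5 = 7.33 g/dL, or platelets at or below 100/1.5 = 66.7 x10^9/L. For neutrophils the rise must exceed 50%, so baseline must be below 1.5/1.5 = 1.0 x10^9/L, which exclusion criterion 10 rules out at entry. For eligible patients the neutrophil endpoint is simply two values above 1500/µL.

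**3. Size, by simulation.** Every distributional input is an assumption. The rule applied is: value above threshold, or at least 1.5 x baseline (more than 1.5 x for neutrophils) if baseline is at or below threshold, at two consecutive assessments out of four. Baseline is measured with the same within-patient error.

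Haemoglobin, between-patient SD 1.8 and within-patient SD 0.6 g/dL:

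| Mean baseline (g/dL) | 10 | 11 | 12 | 13 |
|---|---|---|---|---|
| Improved, no effect | 29% | 50% | 71% | 86% |
| Of these, already above 11 at baseline | 83% | 88% | 92% | 96% |
| Improved, Hb lowered by 1.0 | 14% | 29% | 50% | 71% |
| Improved among observed baseline <=11, no effect | 7% | 12% | 19% | 26% |

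A hand check shows where the first row comes from. The SD of an observed baseline is sqrt(1.8^2 + 0.6^2) = 1.897. The share above 11 is then P(Z > (11 - mean)/1.897), or 29.9%, 50.0%, 70.1% and 85.4% for the four means. The share 'improved' under no effect is almost exactly the share above threshold at entry.

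Neutrophils (log-SD 0.6, within-patient 0.25, entry at least 1.0 x10^9/L), at medians 1.5, 2.5 and 3.5:

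- no effect: 67%, 86% and 94%;
- counts halved: 18%, 42% and 62%.

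Platelets (log-SD 0.6, within-patient 0.2, entry at least 25 x10^9/L), at medians 75, 100 and 150:

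- no effect: 36%, 52% and 76%.

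Medians are before the entry limit is applied.

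**4. Sensitivity, haemoglobin, no effect.** Two assessments per patient give 24% to 81%. Eight give 34% to 89%. Accepting any two of four assessments, not necessarily consecutive, gives 33% to 88%. Patients with fewer than two assessments cannot qualify but stay in the denominator.

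**The case against.** The strongest defence is that the SAP invents nothing. It says improvement means meeting the CR or PR count criteria, and those carry the same absolute threshold with no baseline condition. That is true, but in the protocol the count is one component of a composite: PR also needs at least two tumour-load criteria. Lifted out and renamed as improvement, it loses the part that made it a response.

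Reading C would remove the problem, and the grammar does not quite exclude it. It is strained, though: the clause follows the 50% limb and is the exact complement of the first limb. If C was intended, the text still needs changing.

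Protocol 5.1.2.3 is rationale rather than an endpoint definition, and it speaks of counts below normal, not below the remission thresholds. That stands. The proposed cut-offs follow the SAP's thresholds, and patients between them and the lower limit of normal would appear only as maintained or fell below.

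Other outputs would reveal falls: baseline summaries (SAP 7.1.3), mean counts over time and the neutrophil nadir (SAP 7.5.2), and CTCAE transitions (SAP 7.8.2). They give context but leave the tabulated number uncorrected.

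The percentages are wholly assumption-driven, which is also true. They show direction and plausible size, not a forecast. The consequence is limited as well: there are no formal tests, no key secondary endpoint, and no use of these counts in determining the MTD.

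On growth factors and transfusions, the lead-in arguably imports the protocol's exclusion, and SAP 7.2 already lists G-CSF and transfusions. This is a clarification and the main point does not depend on it. It is still worth settling, because "The use of growth factors such as granulocyte colony stimulating factor (G-CSF) will be allowed".

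**Conclusion.** The concern holds and should be fixed. As written, the three endpoints count patients whose baseline already exceeds the threshold, including those whose counts fall but stay above it. This follows from the wording and needs no assumption beyond the natural reading of the trailing clause.

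The size does rest on assumed baseline distributions. Across those tried, with no drug effect, about 29% to 86% would be tabulated as improved for haemoglobin, 67% to 94% for neutrophils and 36% to 76% for platelets. Harmful effects would still yield sizeable 'improved' counts. The effect is confined to descriptive secondary efficacy tables; the primary DLT and MTD results are untouched.

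**What to change.** In SAP 5.2.2 and 7.5.2:

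1. Restrict numerator and denominator of each improvement endpoint to Treated Set patients at or below the threshold at baseline (haemoglobin 11 g/dL, platelets 100 000/µL, neutrophils 1500/µL).
2. Show patients above the threshold at baseline separately, as maintained or fell below, in line with the lymphocyte split.
3. As a clarification, restate the protocol's support exclusion: growth factors for all three counts, transfusions for haemoglobin and platelets. Fix a look-back window before database lock, and confirm that the ATC codes in SAP 7.2 cover every relevant growth factor.
4. Optionally, list baseline and on-treatment values for each patient counted as improved, so that small drifts such as 10.8 to 11.1 g/dL are visible.

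The cost is SAP text and a small programming change on data already collected. Denominators shrink and the figures will look less favourable.

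The restriction does not remove regression to the mean, and the SAP should say so. Under the same four-assessment assumptions with no effect, about 7% to 26% (haemoglobin), 12% to 24% (platelets) and 29% to 48% (neutrophils) of patients with an observed low baseline would still count as improved. With eight assessments the haemoglobin figure rises to 11% to 36%.

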During the dose-escalation phase, up to 4 courses may be administered. In case of evidence of clinical benefit as judged by the investigator (e.g. PR, CR, disease stabilization, amelioration of CLL related symptoms), treatment with BI 836826 can be continued for another 4 courses after discussion between the Investigator and the Clinical Monitor of the sponsor. During treatment of the expansion cohort, a maximum of 8 courses may be offered to all patients. In the dose-escalation phase as well as in the expansion cohort, in patients who experience sustained benefit and tolerate treatment well, treatment may be continued beyond 8 courses on a case by case basis after discussion between the Investigator and the Clinical Monitor of the sponsor. If patients continue beyond cycle 8, the same assessments will be done as applicable for cycles 5-8. At the end of each treatment course, adverse events and safety laboratory will be assessed. To continue treatment with further courses, **all** of the following criteria must be met:

(1) Neutrophils  $\geq 500 \ /\mu L \ (0.5 \ x \ 10^9/L)$  and platelets  $\geq 25.000 \ /\mu L \ (25 \ x \ 10^9/L)$ , with or without growth-factor support or transfusions.

(2) Acceptable tolerability (in case of an adverse event at the planned start of a treatment course, patients may continue therapy only after recovery to a level which would allow further therapy, i.e. CTCAE grade 1 or pre-treatment value.)

In case criterion 1 and/or 2 is not fulfilled, blood counts and/or the adverse event should be re-evaluated for up to three weeks. Any case of a delay in treatment course should be communicated to the Clinical Monitor at Boehringer Ingelheim. As soon as criterion 1 is met, the investigator in agreement with the Clinical Monitor at Boehringer Ingelheim may continue the treatment (unless other criteria for discontinuation or withdrawal apply, see Section 3.3.4.1). In case an adverse event is continuing at a CTCAE grade 2 or higher without recovery to grade 1 within 5 weeks after the last BI 836826 infusion and this is above the pre-treatment level, the investigator in agreement with the Clinical Monitor at Boehringer Ingelheim may continue BI 836826 only in the case that the event is considered not drug-related by investigator and sponsor.

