7.2 CONCOMITANT DISEASES AND MEDICATION

Only descriptive statistics are planned for this section of the report.

Concomitant therapies (CTh) will be coded according to World Health Organisation Drug Dictionary (WHO DD). They will be classified according to the Anatomical, Therapeutic, Chemical (ATC) classification system. The third ATC level will be used to categorise CThs by therapy type. In situations where a medical product may be used for more than one equally important indication, there are often several classification alternatives. As appropriate, patients receiving CThs with more than one possible ATC level-three category will be counted more than once; footnotes will clarify this possible double counting in tables.

Summaries will be presented for previous and concomitant medications started at baseline and for concomitant therapies started after first administration of the trial medication. Separate summaries will be presented for concomitant medications with missing or incomplete start dates.

Listings of the data will present the concomitant therapy PT and verbatim text as well as the verbatim text of the indication. In addition the listings will include study day for start and stop dates and duration of therapy. Patients with no concomitant therapy will not be included in the listing. A separate listing will be provided for patients receiving Granulocyte-Colony Stimulating Factor (G-CSF) and transfusions (ATC Codes L03AA, B05AA, B05AX).

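### The SAP's blood-count improvement rules omit the protocol's condition on growth factors and transfusions, so supported values can be counted as improved

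*SAP*

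**What the plan says.** SAP 5.2.2 (Other Secondary endpoints, blood counts) defines three endpoints: the number of patients with improved haemoglobin, platelets or neutrophils at two or more response assessments. The lead-in reads "An improvement is indicated by the fulfilment of the criteria for 'Complete Remission' or 'Partial Remission', i.e", followed by three numeric rules. The haemoglobin rule is "Greater than 11g/dL or increase of 50% or more compared to baseline" when haemoglobin is 11 g/dL or lower. The platelet rule is a count above 100 000/µL or "increase of 50% or more compared to baseline if platelets are less than or equal to 100 000" per µL. The neutrophil rule has the same form around 1500/µL.

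Protocol 5.1.2.4.3 gives the haemoglobin criterion for partial remission as "Hemoglobin more than 110 g/L or 50% improvement over baseline (without exogenous growth factors or transfusions"). The platelet criterion carries the same condition and the neutrophil criterion carries it for growth factors. The complete remission criteria in 5.1.2.4.1 have the same pattern.

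On supportive care, protocol 4.2.1 states "The use of growth factors such as granulocyte colony stimulating factor (G-CSF) will be allowed", advises against growth factors in the first course, and lists blood product support among permitted measures. Protocol 4.1.4 lets a further course start on neutrophil and platelet counts "with or without growth-factor support or transfusions". SAP 7.2 plans this output: "A separate listing will be provided for patients receiving Granulocyte-Colony Stimulating Factor (G-CSF) and transfusions".

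**The concern.** The SAP claims to apply the remission criteria but writes down looser ones. The missing condition is what separates recovery of the patient's own blood formation from the effect of a transfusion or G-CSF. Without it, a patient whose low counts needed support can be tabulated as having improved.

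The SAP already accepts the principle at stake. In the same section it discards values taken within 8 days of an infusion, because the immediate change after an infusion does not reflect efficacy. A transfusion or growth-factor effect calls for the same treatment. Protocol 5.1.2.3 treats improving counts as possible patient benefit, so the tables will be read that way.

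**Working it through.** The plan states no figure for these endpoints, so there is none to reproduce. The check is a comparison of texts, followed by simple arithmetic on size.

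**Step 1. Rules side by side.**

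| Parameter | Protocol, CR and PR (5.1.2.4.1, 5.1.2.4.3) | SAP 5.2.2 |
|---|---|---|
| Platelets (B1) | threshold; no growth factors, no transfusion | threshold only |
| Haemoglobin (B2) | threshold; no growth factors, no transfusions | threshold only |
| Neutrophils (B3) | threshold; no growth factors | threshold only |

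**Step 2. Does anything else in the SAP restore the condition?**

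- The sample filter in 5.2.2 requires a value at least 8 days after the last infusion, with a laboratory response assessment reported on treatment and before new CLL therapy. It does not mention support. Response is assessed at the end of each 14-day course, so a supported value at that visit passes.
- The G-CSF and transfusion listing in 7.2 is not linked to the endpoint.
- Section 7.5.2 tabulates the endpoints for the whole Treated Set, with no exclusion, flag or sensitivity analysis for supported patients.
- Section 4.1 describes the redefinition of this endpoint and explains why red blood cells were removed. It does not mention removing the support condition.

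**Step 3. A patient classified differently by the two documents.** Baseline neutrophils are 1.1 × 10⁹/L, which is eligible because exclusion criterion 10 applies below 1.0. On G-CSF the patient reads 1.6 × 10⁹/L at two response assessments.

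- SAP: 1.6 > 1.5, so improved. The relative route is not met (1.6/1.1 = 1.45, a 45% rise), so the patient qualifies through the absolute threshold alone.
- Protocol B3: not met, because of the growth factor.

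**Step 4. Weight of one such patient.** The cohort rate moves by 1/n: 1/3 = 33 points, 1/6 = 17 points, 1/30 = 3.3 points for a full expansion cohort.

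**Step 5. Illustration for the whole trial.** The protocol's expected size is (3×1 + 3×3 + 3×6) + 30 = 60. The documents give neither an improvement rate nor a support rate, so both are assumed. Let p be the proportion improved without support. Let q be the share of the remaining patients who pass a threshold at two assessments only because of support.

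Reported rate = p + (1 − p)q; extra patients = 60(1 − p)q.

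| p | q = 5% | q = 10% | q = 20% |
|---|---|---|---|
| 10% | 14.5% (+2.7) | 19% (+5.4) | 28% (+10.8) |
| 20% | 24% (+2.4) | 28% (+4.8) | 36% (+9.6) |
| 30% | 33.5% (+2.1) | 37% (+4.2) | 44% (+8.4) |

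Across these assumed ranges, about 2 to 11 patients of 60 are added. Since (1 − p)q cannot be negative, the error has one direction.

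**The case against.** **The condition may be imported by reference.** The lead-in names the remission criteria, and the support condition is part of them. A reader might conclude that the SAP chose to count supported values; the documents show no such decision, only an incomplete restatement. This stands as a point about intent. It does not settle the matter, because the numeric rules are what will be programmed, and no look-back window exists with which to apply an implied condition.

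**The protocol's own blood-count endpoint has no such condition.** Protocol 5.1.1 and 5.1.2.3 list blood counts without it. That is correct, so the conflict is between the SAP and the remission criteria it chose to borrow.

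**Supported values need not be common.** A reader might infer from the retreatment rule in protocol 4.1.4 that supported values are to be expected at these visits. The rule permits them but does not show them. Its levels are 0.5 and 25 × 10⁹/L, a third and a quarter of the improvement thresholds (0.5/1.5 and 25/100), and it sets no haemoglobin level. The advice against growth factors in course 1 and the two-assessment requirement also make a single transient rise less likely to qualify. These points reduce the likely size without closing the route.

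**Other outputs show the toxicity.** Neutropenia and thrombocytopenia episodes, neutrophil nadir, mean counts by cohort and the support listing are all planned. They help a careful reader but do not correct the endpoint.

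**Conclusion.** The point holds as a defect in the rule: followed literally, SAP 5.2.2 can count supported values as improved where the criteria it cites would not. The bias can only be upward. It matters most in cohorts of 3 or 6, where one patient moves the rate by 33 or 17 points. Its frequency is unknown, and the 2 to 11 extra patients rest entirely on the assumed p and q.

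Two stronger readings are not supported. One is that supportive-care effects will in fact be reported as drug benefit; the documents show only that they can be. The other is that the bias grows with marrow toxicity and so reverses the dose pattern. That would need support use to rise with dose, and no figure in the documents bears on this; it remains a possibility.

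The consequences are confined to three descriptive secondary endpoints. The MTD and DLT analysis does not use them. Best overall response is assessed by the investigator under the response guidelines rather than derived from these rules. The point is worth correcting before database lock but does not threaten the primary objective.

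**What to change.** - In SAP 5.2.2, add the protocol condition to each rule: for haemoglobin and platelets, no exogenous growth factor and no transfusion; for neutrophils, no growth factor.
- Identify supported values from the concomitant-therapy dates that protocol 4.2.1 already requires, using one look-back window fixed before database lock. The documents give no length for it, so the sponsor must set and justify one. State how incomplete dates are handled, and note that after the end-of-treatment visit only therapy given for an adverse event is recorded.
- Confirm the code list. SAP 7.2 names L03AA, B05AA and B05AX and describes them as covering G-CSF and transfusions. The protocol condition covers all exogenous growth factors, and the documents do not show that these codes do.
- Do not count supported values towards improvement, and show the unrestricted count as a sensitivity row.

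The cost is a few lines of SAP text, a check of the code list, and a merge of laboratory and concomitant-therapy data. The downside is a possibly lower improvement count and dependence on one pre-set window.
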